### 6.2.3.2 Time to first prostate cancer-related invasive procedures

Time to first prostate cancer-related invasive procedure is defined as time from randomization to date of first prostate cancer-related invasive procedure.

Prostate cancer-related invasive procedure is defined as any procedure needed for alleviation of symptoms, signs or findings caused by progression of prostate cancer (e.g. catheterization of the bladder, percutaneous drainage of hydronephrosis, palliative electro resection of the prostate, etc.).

Status of prostate cancer-related invasive procedures will be assessed from randomization until the first prostate cancer-related invasive procedure, i.e. until end of follow-up period.

Patient with no prostate cancer-related invasive procedure will be censored.

Table 15 will be used for calculating the time to first prostate cancer-related invasive procedure.  $\text{Time Cancer-related invasive procedure} = \text{End Date} - \text{Date of randomization} + 1$ .

**Table 15: Censoring Rules for prostate cancer-related invasive procedure**

Situation	End Date on or prior to cut-off date	Censored
Recorded prostate cancer-related invasive procedure during the study	Date of the first assessment that qualified as prostate cancer-related invasive procedure	No
Death during the study before prostate cancer-related invasive procedure	Date of the last visit at which prostate cancer-related invasive procedure question was collected or randomization date whatever comes later	Yes
Patient has no recorded prostate cancer-related invasive procedure at data cut-off	Date of last visit at which prostate cancer-related invasive procedure question or randomization date whatever comes later	Yes
Patient lost to follow-up before data cut-off	Date of last visit at which prostate cancer-related invasive procedure question or at the data cut-off, whichever occurs first	Yes

This endpoint is selected from the ADTTE dataset using variable PARAMCD equal to 'CRIP'.

A log rank test stratified by same stratification factors used in the MFS analysis will be used to compare the darolutamide treated and placebo groups.

The hazard ratio as well as its 95% CI will be generated with a Cox regression model as for MFS.

Kaplan-Meier survival curves (product-limit estimates) will be presented by treatment arm. The Kaplan-Meier estimate of the median time to first prostate cancer-related invasive procedure and first and third quartiles will be presented with 95% CI.

### 6.2.3.3 Time to initiation of subsequent antineoplastic therapy

Time to initiation of subsequent antineoplastic therapy is defined as time from randomization to initiation of first antineoplastic therapy.

Subsequent antineoplastic therapy will be assessed from the first follow-up visit until the first use of such therapy. Patients who do not reach the endpoint or died will be censored.

Antineoplastic therapy will be selected using:

- ATC code class L (antineoplastic and immunodulating agents): L01 Antineoplastic agents (except cytotoxic chemotherapy L01A, L01B, L01C, L01D and L01X), L02 endocrine therapy and L03 immunostimulants,

- ATC code class H: H02Corticosteroids for systemic use.

The list of antineoplastic therapy is available in Appendix 9.8.

Table 16 will be used for calculating the time to initiation of subsequent antineoplastic therapy. Time to initiation of subsequent antineoplastic therapy event = End Date-Date of randomization +1.

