5.7.2 Prohibited treatments

Initiation of the following medications before the first metastasis, either during or after the study treatment period is prohibited:

- Any investigational medicinal product
- Radiopharmaceuticals
- Immunotherapy (e.g. sipuleucel-T)
- Cytotoxic chemotherapy and any other systemic antineoplastic therapy
- Enzalutamide, ARN-509, bicalutamide, flutamide, nilutamide
- Cyproterone acetate, estrogen
- 5 α -reductase inhibitor
- Abiraterone acetate, TAK-700 or other CYP17 inhibitors
- Systemic ketoconazole (as antineoplastic therapy)
- Osteoclast-targeted therapy such as bisphosphonate or denosumab. Patients receiving treatment with osteoclast-targeted therapy at a dose and schedule indicated for osteoporosis prior to study entry may continue treatment at the same dose and schedule.
- Continuous use of systemic corticosteroid with dose greater than the equivalent 10 mg of prednisone/prednisolone per day. Short-term use of systemic corticosteroids with higher doses up to 28 days during the study treatment period is allowed, but treatment should be kept as short as possible.

Another systemic antineoplastic therapy may be initiated no sooner than 7 days after the last dose of study treatment.

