 - ¹³ Blood (plasma) sampling for tumour-related biomarker evaluation will be collected on day 1 visit before study treatment administration, at the start of open-label treatment visit, and at the end-of-study treatment visit unless precluded by local guidelines, e.g. IEC/IRB or regulatory authorities. For placebo patients crossing over to open-label darolutamide treatment, sampling will not be performed at the end-of-study treatment visit (see [Table 4](#)).
 - ¹⁴ The local PSA result taken at screening should be used to confirm the patient has CRPC (inclusion criterion 4) and meets inclusion criterion 6.
 - ¹⁵ Only study drug accountability performed at the end-of-study treatment visit.
 - ¹⁶ A blood sample for DNA extraction will be taken at day 1 visit (or later during the study if feasible) only from patients who have signed the PG IC unless precluded by local guidelines, e.g. IEC/IRB or regulatory authorities.
 - ¹⁷ 12-lead ECG will be performed only at the start of open-label visit. ECG is not required on subsequent visits during the open-label darolutamide treatment.
 - ¹⁸ Survival data will also be collected through an additional survival sweep. All patients considered alive shortly after the database cut-off date for the MFS analysis and prior to any subsequent analysis of OS will be contacted for survival status.

Table 4. Study event schedule after withdrawal of study treatment or during the follow-up period; and study event schedule for placebo patients crossing over to open-label darolutamide treatment

Protocol activities	For patients discontinuing study drug before confirmed metastasis and not initiating any prohibited treatment *	For patients after confirmed metastasis, or receiving subsequent treatment after unblinding *	For placebo patients crossing over to open-label darolutamide	
	Visits Every 16 weeks (±7 days) from end-of-study treatment visit ¹	Visits or phone contacts Every 16 weeks (±7 days) from end-of- study treatment visit ²	Visits Every 16 weeks (±7 days) from start of open-label treatment visit ¹	End-of-study treatment visit 28 days (+7 days) after last dose or in transition to roll-over study
BPI-SF	X	X	X	X
Dispensing of pain diary	X	X	X	X
Collection of pain diary and pain medications	X ³	X ³	X ³	X
PCS subscale of FACT-P	X	X	X	X
ECOG performance status	X	X	X	X
Use of subsequent antineoplastic therapies	X	X	X	X
Laboratory safety assessments			X	X

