6.3.3.3 Time to initiation of subsequent antineoplastic therapy

Time to initiation of subsequent antineoplastic therapy is defined as time from randomisation to initiation of first antineoplastic therapy.

Subsequent antineoplastic therapy will be assessed from the first follow-up visit until the first use of such therapy.

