### 6.2.2.3 Time to initiation of first cytotoxic chemotherapy

The time to cytotoxic chemotherapy (CYTOC) is defined as time from randomization to the start of the first cytotoxic chemotherapy cycle. Patients who have not taken cytotoxic chemotherapy will be right censored at their last visit.

Cytotoxic chemotherapy drugs are defined with ATC code L01A, L01B, L01C, L01D and L01X. The list of all cytotoxic chemotherapy is available under Appendix 9.7.

If the complete date of the cytotoxic chemotherapy is not known, but the year and month are available, day 15 of the month will be used for the calculation.

Table 11 will be used for calculating the time to first cytotoxic chemotherapy. Time to cytotoxic chemotherapy = End Date – Date of Randomization +1.

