**Table 11: Censoring Rules for Cytotoxic Chemotherapy**

Situation	End Date on or prior to cut-off date	Censored
Recorded cytotoxic chemotherapy during the study	Date of the first assessment that qualified as cytotoxic chemotherapy	No
Death during the study before cytotoxic chemotherapy	Date of last visit at which cytotoxic chemotherapy question was collected or randomization date whatever comes later	Yes
Patient has no recorded cytotoxic chemotherapy at data cut-off	Date of last visit at which cytotoxic chemotherapy question was collected or randomization date whatever comes later	Yes

Patient lost to follow-up before data cut-off	Date of last visit at which cytotoxic chemotherapy question was collected or randomization date whatever comes later	Yes
---	--	-----

Cytotoxic chemotherapy is a specific antineoplastic therapy and therefore the CRF question “Has the patient taken any new antineoplastic therapy since previous visit?” implies the question for cytotoxic chemotherapy.

This endpoint is selected from the ADTTE dataset using variable PARAMCD equal to ‘CYTOC’.

A log rank test stratified by stratification factor of PSADT ( $\leq 6$  vs.  $> 6$  months) and use of osteoclast-targeted therapy (yes vs. no) at randomization will be used to compare the darolutamide treated and placebo groups.

The hazard ratio as well as its 95% CI will be presented based on fitting a Cox regression model with treatment as factor and stratified by PSADT ( $\leq 6$  vs.  $> 6$  months) and use of osteoclast-targeted therapy (yes vs. no) at randomization.

Kaplan-Meier survival curves (product-limit estimates) will be presented by treatment arm. The Kaplan-Meier estimate of the median survival time and first and third quartiles will be presented with 95% CI. Greenwood's formula will be used for the standard error of the Kaplan-Meier estimate in the calculation of these confidence limits.

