**Table 16: Censoring Rules for antineoplastic therapy**

Situation	End Date on or prior to cut-off date	Censored
Recorded antineoplastic therapy during the study	Date of the first assessment that qualified as antineoplastic therapy	No
Death during the study before antineoplastic therapy	Date of last visit at which antineoplastic therapy question was collected or randomization date whatever comes later	Yes
Patient has no recorded antineoplastic therapy at data cut-off	Date of last visit at which antineoplastic therapy question was collected or randomization date whatever comes later	Yes
Patient lost to follow-up before data cut-off	Date of last visit at which antineoplastic therapy question was collected or at the data cut-off, whichever occurs first	Yes

This endpoint is selected from the ADTTE dataset using variable PARAMCD equal to 'ISAT'.

A log rank test stratified by same stratification factors used in the MFS analysis will be used to compare the darolutamide treated and placebo groups.

The hazard ratio as well as its 95% CI will be generated with a Cox regression model as for MFS.

Kaplan-Meier survival curves (product-limit estimates) will be presented by treatment arm. The Kaplan-Meier estimate of the median time to initiation of subsequent antineoplastic therapy and first and third quartiles will be presented with 95% CIs.

A summary of first subsequent antineoplastic therapy will be provided.

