### 9.7 Cytotoxic chemotherapy: time to cytotoxic chemotherapy

The cytotoxic chemotherapy was selected in CM dataset (ATC code L01A, L01B, L01C, L01D, and L01X). ). Sponsor's assessment of cytotoxic chemotherapy is presented in a supplementary document.

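### The code list for time to subsequent antineoplastic therapy removes all cytotoxic chemotherapy, so it does not measure the endpoint as named and defined

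*SAP*

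**What the plan says.** **Definition.** Protocol 6.3.3.3 gives the endpoint as "defined as time from randomisation to initiation of first antineoplastic therapy". SAP 6.2.3.3 uses the same definition. Neither restricts it to non-cytotoxic drugs.

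**Selection rule.** SAP 6.2.3.3 selects from ATC class L "L01 Antineoplastic agents (except cytotoxic chemotherapy L01A, L01B, L01C, L01D and L01X), L02 endocrine therapy and L03 immunostimulants", and from class H the systemic corticosteroids (H02). Appendix 9.8 repeats the list and adds that the sponsor's assessment of these therapies is in a supplementary document, which is not among the documents reviewed.

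**Chemotherapy codes.** For the secondary endpoint, SAP 6.2.2.3 states: "Cytotoxic chemotherapy drugs are defined with ATC code L01A, L01B, L01C, L01D and L01X". Appendix 9.7 lists the same five codes.

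**Where the documents place chemotherapy.**
- The note below SAP Table 11 says "Cytotoxic chemotherapy is a specific antineoplastic therapy" and relies on the CRF question about new antineoplastic therapy to capture it.
- Protocol 5.7.2 lists "Cytotoxic chemotherapy and any other systemic antineoplastic therapy" as one group.
- Protocol Table 4 has a row "Use of subsequent antineoplastic therapies" and no separate chemotherapy row.
- SAP Appendix 9.6 (prohibited medication) takes all of ATC class L except L02AE, so chemotherapy is included there.

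**Censoring.** SAP Table 16 has the row "Patient has no recorded antineoplastic therapy at data cut-off". Such patients are censored at the last visit at which the question was asked, or at randomisation if later.

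**The concern.** The rule and the definition describe different events. A man who starts chemotherapy has started a subsequent antineoplastic therapy by the definition, by the CRF question and by the SAP's own statement. The code list nevertheless treats him as not having had the event, while a systemic corticosteroid does count.

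The result reported under this endpoint's name would therefore omit some first therapies and date others late. This affects the Kaplan-Meier estimates, the hazard ratio and the planned tabulation of which therapy came first. A reader would take them to cover all subsequent therapy.

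**Working it through.** The plan gives no figure to reproduce here. The check compares the lists, applies the rule to example patients, and then gives an illustration of size.

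**1. The two code lists**

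| Source | Codes |
|---|---|
| Chemotherapy, SAP 6.2.2.3 and Appendix 9.7 | L01A, L01B, L01C, L01D, L01X |
| Excluded, SAP 6.2.3.3 and Appendix 9.8 | L01A, L01B, L01C, L01D, L01X |

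The sets are identical, so all chemotherapy as the SAP defines it is removed.

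**2. The rule applied to example patients** (invented days; last visit day 700)

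| Patient | As coded | As defined |
|---|---|---|
| Chemotherapy day 300 only | censored day 700 | event day 300 |
| Chemotherapy day 300, L02 drug day 500 | event day 500 | event day 300 |
| L02 drug day 300, chemotherapy day 500 | event day 300 | event day 300 |
| Chemotherapy and H02 both day 300 | event day 300 | event day 300 |

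The first patient has an antineoplastic therapy recorded on the CRF, yet the code list puts him in the Table 16 row for patients with none.

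**3. Illustration of size.** Every input is an assumption:
- *s*: share of first subsequent therapies that are chemotherapy (5%, 20%, 40%, 60%).
- *h*: share of those with an H02 drug recorded as starting with the chemotherapy.
- *f*: share of the remainder who later take a listed drug, after an exponential delay of mean 6 months (rate μ = 1/6).
- True time to first therapy exponential with median 25 months, so λ = ln 2 / 25 = 0.02773. The plan uses 25 months as the placebo MFS median; it is borrowed here only as a scale.
- Everyone is followed to 72 months, the protocol's estimated maximum per patient, with no other censoring.

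With r = s(1−h), S₁(t) = exp(−λt) and S₂(t) = [μ exp(−λt) − λ exp(−μt)] / (μ−λ), the curve as coded is

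S(t) = (1−r) S₁(t) + r f S₂(t) + r(1−f),

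and the share of events lost is [S(72) − S₁(72)] / [1 − S₁(72)].

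Example, s = 0.4, h = 0, f = 0.5: S₁(72) = 0.1358 and S₂(72) = 0.1630. So S(72) = 0.6 × 0.1358 + 0.2 × 0.1630 + 0.2 = 0.3141, and the loss is (0.3141 − 0.1358) / 0.8642 = 0.206.

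Example median, s = 0.2, h = 0, f = 0: 0.2 + 0.8 exp(−λt) = 0.5 gives exp(−λt) = 0.375 and t = 35.4 months.

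Share of events lost, then apparent median in months:

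| h, f | s = 5% | s = 20% | s = 40% | s = 60% |
|---|---|---|---|---|
| 0, 0 (upper bound) | 5%; 27.0 | 20%; 35.4 | 40%; 64.6 | 60%; not reached |
| 0, 0.5 | 2.6%; 26.1 | 10.3%; 30.0 | 20.6%; 37.1 | 30.9%; 48.1 |
| 0.5, 0.5 | 1.3%; 25.5 | 5.2%; 27.3 | 10.3%; 30.0 | 15.5%; 33.2 |
| 0.8, 0 | 1.0%; 25.4 | 4.0%; 26.5 | 8.0%; 28.3 | 12.0%; 30.3 |
| 0.8, 0.5 | 0.5%; 25.2 | 2.1%; 25.9 | 4.1%; 26.8 | 6.2%; 27.8 |

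No hazard ratio is computed, because it would need the chemotherapy share in each arm.

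**The case against.** The exclusion looks deliberate: it names chemotherapy, lists all five codes and appears twice. Chemotherapy has its own, higher-ranked endpoint, and protocol 7.7.3 leaves the details of additional analyses to the SAP. On this reading only the label is at fault. Part of this stands, since the exclusion may well be intended. But the SAP gives no reason, the name and definition were not narrowed, and Table 16 does not say what happens to a patient with earlier chemotherapy. A separate endpoint does not require exclusion here either: opioid initiation is part of pain progression and is also analysed alone in SAP 6.2.3.8.

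The final event set also depends on the sponsor's assessment named in Appendix 9.8, which might restore chemotherapy. That stands as a condition on the conclusion. The SAP gives no criteria for the assessment, and one that restored chemotherapy would contradict the written rule.

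The size figures rest wholly on assumed inputs. That is correct. At a 5% share the effect is slight, and with shorter follow-up the longer medians would not be observed. The table shows the mechanism and is not a prediction.

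Finally, patients who start a prohibited therapy before metastasis are followed only for survival under protocol section 3 (section 4.7.2 reads differently), so a later listed drug may go unrecorded. This is true, but it moves such patients towards the upper bound.

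**Conclusion.** The concern holds. As written, the selection rule does not measure the endpoint that both documents define. Unless the sponsor's separate assessment reverses the rule, chemotherapy-only patients are censored, and patients with chemotherapy first are dated to a later listed drug if one is recorded. The exception is a listed drug, such as a corticosteroid, starting by the same date.

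The mismatch is certain from the text; the number of events affected is not. It depends on the chemotherapy share, on corticosteroid recording and on later therapy, none of which the documents give. The direction of any effect on the hazard ratio is unknown.

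Severity is minor. SAP 6.2.3 gives tertiary p-values an informative role only, chemotherapy starts are still analysed under 6.2.2.3, and MFS, OS and the secondary hierarchy do not use this list.

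**What to change.** Add L01A, L01B, L01C, L01D and L01X to the selection in SAP 6.2.3.3 and Appendix 9.8, and to the tabulation of first subsequent therapy.

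If the exclusion is intended, rename and redefine the endpoint as time to first non-cytotoxic antineoplastic therapy, give the reason, and state in Table 16 how an earlier chemotherapy start is handled.

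The cost is SAP wording and a code-list edit. The data are already collected, and the chemotherapy records are already selected under Appendix 9.7.

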5.7 Prior, concomitant and follow-up treatments

5.7.1 Prior and concomitant treatments

History of all prostate cancer treatments, including radiotherapy, before the time of IC must be recorded on the CRFs.

All concomitant treatments from the time of IC until the end-of-study treatment visit must be recorded on the CRFs. Contrast media do not need to be recorded as concomitant medication unless there is an adverse event related to its administration (e.g. allergic reaction). Once the patient has been withdrawn from study treatment, follow-up treatments will be recorded if used to treat new related or unresolved related AEs or if it is a systemic antineoplastic therapy.

Patients who have not undergone bilateral orchiectomy must continue GnRH agonist or antagonist therapy during the study.

The patient must not have been administered another investigational drug within 28 days before randomisation.

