**9.6 Prohibited medication: metastasis-free survival**

Following medications considered prohibited was selected in CM dataset:

- Radiopharmaceuticals (ATC codes V10BX, V10XX03),
- Immunotherapy (e.g. sipuleul T) (ATC code L03),
- Cytotoxic chemotherapy and any other systemic antineoplastic therapy (ATC code class L: antineoplastic and immunodulating agents , with the exception of L02AE (Gonadotropin-releasing hormone analogues)),
- Enzalutamide, ARN-509, bicalutamide, flutamide, nilutamide (ATC code L02B),
- Cyproterone acetate estrogen (ATC codes G03H, G03C),
- 5  $\alpha$ -reductase inhibitor (ATC code G04CB),
- Abiraterone acetate, TAK-700 or other CYP17 inhibitors (ATC code L02B),
- Systemic ketoconazole (as antineoplastic therapy) (ATC codes D01AC08; G01AF11, J02AB02),
- Osteoclast-targeted therapy such as bisphosphonate or denosumab (ATC code M05B) given for preventing skeletal-related events. These drugs are allowed for treatment of osteoporosis,
- Continuous use of systemic corticosteroid (ATC code H02).

Sponsor's assessment of prohibited medication is presented in a supplementary document.

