### 9.8 Antineoplastic therapy: time to initiation of subsequent antineoplastic therapy

- Antineoplastic therapy treatment was selected in CM dataset
- ATC code class L (antineoplastic and immunodulating agents): L01 Antineoplastic agents (except cytotoxic chemotherapy L01A, L01B, L01C, L01D and L01X), L02 endocrine therapy and L03 immunostimulants
- ATC code class H: H02Corticosteroids for systemic use.

Sponsor's assessment of antineoplastic therapy is presented in a supplementary document.

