## 9.12 GnRH agonist/antagonist therapy

The GnRH antagonist treatments were selected in CM dataset (ATC code starting with L02AE, H01CA and L02BX).

L02AE Gonadotropin releasing hormone analogues (L02AE01 buserelin, L02AE02 leuprorelin, L02AE03 goserelin, L02AE04 triptorelin, L02AE05 histrelin), H01CA Gonadotropin releasing hormones, L02BX Other hormone antagonists and related agents (L02BX01 abarelix, L02BX02 degarelix, L02BX03 abiraterone (except if used as previous therapy)).

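### The code list for time to subsequent antineoplastic therapy has no GnRH exclusion and no steroid indication limit, so background treatment can be scored as the event

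*SAP*

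**What the plan says.** - **Definition.** SAP 6.2.3.3 has the endpoint "defined as time from randomization to initiation of first antineoplastic therapy". On timing it adds: "Subsequent antineoplastic therapy will be assessed from the first follow-up visit until the first use of such therapy". Protocol 6.3.3.3 agrees on both.
- **Code list.** SAP 6.2.3.3 and Appendix 9.8 take L01 less five cytotoxic groups, then "L02 endocrine therapy and L03 immunostimulants", then "ATC code class H: H02Corticosteroids for systemic use". The cytotoxic groups are the only exception written.
- **Where GnRH drugs are coded.** Appendix 9.12 lists "L02AE Gonadotropin releasing hormone analogues" along with H01CA and L02BX. Within L02BX it names abarelix (01), degarelix (02) and abiraterone (03).
- **The comparable list for MFS.** Appendix 9.6 takes class L "with the exception of L02AE (Gonadotropin-releasing hormone analogues".
- **Background therapy.** Protocol 5.7.1: "Patients who have not undergone bilateral orchiectomy must continue GnRH agonist or antagonist therapy during the study".
- **Steroids.** Protocol 5.7.2 prohibits only continuous use above a stated dose. It adds: "Short-term use of systemic corticosteroids with higher doses up to 28 days during the study treatment period is allowed".
- **Event row.** Table 16 scores any antineoplastic therapy recorded during the study. It repeats neither the follow-up window nor any condition that the therapy be new.
- **Review step.** Appendix 9.8 says that the sponsor's assessment of these drugs is in a supplementary document, which is not among those supplied.
- **Status.** SAP 6.2.3 treats p-values for these endpoints as informative only.

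**The concern.** The endpoint is meant to show how long men go before further anticancer treatment begins. GnRH therapy is part of the background in both arms, and a steroid given for an adverse event is not anticancer treatment. A code list that admits either can turn a censored man into an event, or bring his event date forward, for reasons unrelated to his cancer treatment.

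Three reported outputs depend on the list: the Cox hazard ratio with its stratified log-rank test, the Kaplan-Meier estimates, and the summary of first subsequent therapies. The last would be wrong on its face if it listed a GnRH injection or an adverse-event steroid as a first subsequent cancer treatment, whatever happened to the hazard ratio.

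**Working it through.** The plan states no event count, assumed effect or misclassification rate for this endpoint, so there is no figure to reproduce. The check sets the code list against the definition and the recording rules.

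**Step 1: which records can reach the event.** Protocol 5.7.1 records all concomitant treatments from consent to the end-of-study treatment visit. After withdrawal from study treatment it records only drugs for related adverse events and systemic antineoplastic therapy. SAP 6.2.2.3 describes the CRF question as asking about new antineoplastic therapy since the previous visit.

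| Record | In code list | Recorded | Removed by a written rule |
|---|---|---|---|
| GnRH, one continuous record begun before randomisation | Yes (L02AE or L02BX) | Yes | Yes: not an initiation |
| GnRH switch, restart or re-entered record on treatment | Yes | Yes | Only if the window acts as a filter on start dates |
| The same, in follow-up | Yes | If the site reports it as new antineoplastic therapy | No |
| Steroid course begun on treatment | Yes (H02) | Yes | Only if the window acts as a filter on start dates |
| Steroid in follow-up for a related adverse event | Yes (H02) | Yes | No |
| Steroid in follow-up for an unrelated condition | Yes (H02) | Not required | Not applicable |

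GnRH drugs coded H01CA fall outside both L02 and H02, so they cannot enter.

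**Step 2: can the window act as a date filter?** Protocol 5.7.2 and 6.1.2.6 allow another systemic antineoplastic therapy from 7 days after the last dose. The end-of-study treatment visit is at 28 days (+7), and Table 4 places follow-up every 16 weeks from that visit.

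- First follow-up visit, nominally: 28 + 16 × 7 = 140 days after the last dose.
- Gap from the earliest permitted new therapy: 140 − 7 = 133 days.

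A strict filter would drop or misdate genuine therapies begun in those 133 days. The window therefore reads better as when the question starts to be asked. Table 16, which 6.2.3.3 names as the basis for the calculation, does not contain it. A programmer working from Table 16 and Appendix 9.8 would be able to reach on-treatment records.

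**Step 3: size and direction.** Suppose false records occur at the same hazard in both arms from randomisation and make up a share q of the scored placebo hazard. Then:

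scored HR = (1 − q) × true HR + q

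| Assumed true HR | q = 10% | q = 25% | q = 50% |
|---|---|---|---|
| 0.40 | 0.46 | 0.55 | 0.70 |
| 0.65 | 0.685 | 0.74 | 0.825 |

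Every input here is an assumption, so the table shows a mechanism and is not an estimate. The equal-hazard premise also fails if false records count only in follow-up. Men leave study treatment at confirmed metastasis, and under the trial's own hypothesis that comes sooner on placebo. False records would then start earlier on placebo, and the bias need not be towards 1.

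**The case against.** The strongest reply is that the code list is not the whole rule. The event is an initiation, the assessment starts at follow-up, and the CRF asks about new therapy. The higher-dose steroid allowance in Protocol 5.7.2 is confined to the study treatment period, before that window opens. A sponsor assessment also stands between the list and the event.

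Other appendices suggest that the lists are first-pass filters. Appendix 9.10 takes all of N02A for cancer-pain opioids. Appendix 9.6 uses H02 for continuous steroid use, which an ATC code cannot show, and its exemption leaves the GnRH antagonists in L02BX inside class L.

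Much of this stands. A reader might infer that mandatory GnRH therapy and every permitted steroid course automatically count as the event. The documents do not support that: GnRH therapy continuing from before randomisation is not initiated afterwards, and on-treatment steroids precede the stated assessment period.

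The reply does not close the gap. Step 2 shows that the window cannot safely serve as a date filter, and Table 16 omits it. A switch, restart or re-entered record has a start date after randomisation, and the word *new* does not clearly rule out a new GnRH product. Appendix 9.8 gives no criteria for the assessment and does not say whether it is made blind. Appendix 9.6 refers to the same kind of assessment and still writes out its L02AE exemption, so the authors did not treat review as a substitute for the rule there.

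**Conclusion.** The written rule is incomplete, and it is inconsistent with Appendix 9.6. A GnRH switch, restart or re-entered record after randomisation, or a systemic steroid given for an adverse event, can be scored as a first subsequent antineoplastic therapy. Whether any such record survives depends on a sponsor assessment whose content is unknown.

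The effect on the hazard ratio, the Kaplan-Meier estimates and the summary of first therapies cannot be calculated from the documents. A reader might infer a known dilution towards 1. That requires equal false-event hazards from randomisation, which the documents do not establish.

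Severity is minor. The endpoint is tertiary, lies outside the hierarchical testing in SAP 6.2.2, and bears on no confirmatory conclusion.

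**What to change.** - In SAP 6.2.3.3 and Appendix 9.8, exclude GnRH agonists and antagonists: L02AE, L02BX01 and L02BX02. Keep abiraterone (L02BX03) as an event; excluding L02BX as a whole would lose it.
- Count H02 only when the record shows antineoplastic treatment, not an adverse event or other condition. The documents do not show a CRF indication field for these records. If there is none, state the review rule to be used instead.
- Align the event row of Table 16 with 6.2.3.3, so that it requires a newly initiated subsequent therapy. Say whether the first follow-up visit limits start dates or only marks when the question is first asked.
- State the criteria for the sponsor's assessment, and apply all of these rules before treatment assignment is known.

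The cost is a wording change, a short code-list edit and a small amount of record review for H02 entries. No new data are needed if the indication is already recorded.
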